2. STUDY OBJECTIVES

The primary objectives of the study are:

- to assess the effect of food on the PK of LOXO-305 administered under fasted conditions and after a standard meal in healthy adult subjects
- to assess the effect of a gastric pH change on the PK of LOXO-305 after multiple-doses of a proton pump inhibitor (PPI) (omeprazole) in healthy adult subjects.

The secondary objective of the study is:

- to determine the safety and tolerability of a single dose of LOXO-305 administered with and without food and in the presence of a PPI (omeprazole) in healthy adult subjects.

3. STUDY ENDPOINTS

The following PK parameters will be calculated whenever possible, based on the plasma concentrations of LOXO-305 (as appropriate):

- area under the concentration-time curve from Hour 0 to 24 hours postdose, as calculated by the linear trapezoidal method (AUC₀₋₂₄)

- area under the concentration-time curve from Hour 0 to the last measurable concentration (AUC_{0-t})
- area under the concentration-time curve extrapolated to infinity (AUC_{0-inf})
- extrapolation for area under the concentration-time curve (%AUC_{Extrap})
- maximum observed plasma concentration (C_{max})
- time to maximum observed concentration (t_{max})
- apparent terminal elimination rate constant (λ_Z)
- apparent systemic clearance (CL/F)
- apparent terminal elimination half-life (t_{1/2}).

Safety and tolerability will be assessed by monitoring adverse events (AEs), performing physical examinations and clinical laboratory tests, measuring vital signs, and 12-lead electrocardiograms (ECGs).

4. STUDY DESIGN

This is a Phase 1, open-label, randomized, 2-way crossover, 3-period study. A single oral dose of LOXO-305 will be administered under fasted conditions (Treatment A) and fed conditions (Treatment B). Multiple oral doses of omeprazole will be administered once daily from Day 15 through Day 18, with a single oral dose of LOXO-305 co-administered with omeprazole under fasted conditions on Day 18 (Treatment C). PK sampling will be obtained for 168 hours after administration of each dose of LOXO-305 (ie, on Days 1, 8, and 18). The 2 treatment sequences will be ABC and BAC. Subjects will be randomly assigned to 1 of the 2 treatment sequences, according to a randomization scheme issued by Covance.

In Treatment A, a single oral dose of 200 mg LOXO-305 will be administered in the morning on Day 1 or Day 8 (according to the randomization scheme), following a fast of at least 10 hours prior to and 4 hours after dosing. In Treatment B, a single oral dose of 200 mg LOXO-305 will be administered in the morning on Day 1 or Day 8 (according to the randomization scheme), approximately 30 minutes after starting a standard breakfast. In Treatment C, a single oral dose of 40 mg omeprazole will be administered in the morning on Days 15, 16 and 17, following a fast of at least 8 hours prior to omeprazole dosing, followed by a standard breakfast administered approximately 1 hour after dosing. On Day 18, a single oral dose of 40 mg omeprazole will be co-administered with a single oral dose of 200 mg LOXO-305 in the morning, following a fast of at least 10 hours prior to and 4 hours after omeprazole and LOXO-305 co-administration. Standard breakfasts should be entirely consumed within 30 minutes. Serial PK blood samples for the analysis of plasma concentrations of LOXO-305 will be collected from predose through 168 hours postdose for each treatment.

There will be a washout period of 7 days between the doses of LOXO-305 administered in Treatments A and B, and a washout period of 7 days between the doses of LOXO-305 administered in Treatments A or B and the first dose of omeprazole in Treatment C.

To assess their eligibility to enter the study, potential subjects will be screened within 28 days (Days -29 to -2) and be admitted to the Clinical Research Unit (CRU) on Day -1 (Check-in). Replacement subjects may be enrolled only if deemed necessary by the Sponsor.

Subjects will be confined at the CRU from the time of Check-in (Day -1) until End of Treatment (EOT) on Day 25 upon completion of all PK and safety assessments or Early Termination (ET) if the subject discontinues. A follow-up phone call will occur for all subjects who received at least 1 dose of study drug (including subjects who are terminated early) 7 days (\pm 2 days) after EOT or ET.

The start of the study is defined as the date the first subject who is enrolled in the study signs an Informed Consent Form (ICF). Note that enrolled subjects are defined as those subjects who are assigned a dose of study drug; this definition excludes screen failure subjects.

In this study, physical examinations, 12-lead ECGs, vital signs, How Do You Feel? inquiries, clinical chemistry panel, coagulation parameters, creatine kinase, complete blood count, urinalysis and recording of concomitant medications will be performed at specified times during the study. The AEs and serious adverse events (SAEs) will be collected beginning at informed consent. The AEs will be reported throughout the study (ie, from signing of the ICF until End of Study [EOS], or until ET if the subject discontinues from the study and does not complete a follow-up phone call), either as subject medical history (if the event is reported as beginning prior to signing of the ICF or if the event occurs prior to study drug administration on Day 1 and is assessed as not related to study procedures by the Investigator [or designee]) or as AEs (if the event occurs after signing of the ICF but prior to study drug administration on Day 1 and is assessed as related to study procedures by the Investigator [or designee], or if the event occurs after study drug administration on Day 1 through EOT or ET regardless of relationship to study drug). From EOT or ET through EOS, only AEs assessed as related to study drug by the Investigator (or designee) are to be reported. All SAEs that develop from the time of ICF signing until EOS (or ET, if the subject discontinues from the study and does not complete a follow-up phone call) are to be reported. Study completion is defined as the time of the last subject's follow-up phone call.

5. SAMPLE SIZE JUSTIFICATION

CCI

This is a phase 1 study and the sample size is not based upon any formal power calculations but is consistent with previous studies of a similar design.

Every attempt will be made to enroll at least 2 subjects of each sex in the study.

6. STUDY TREATMENTS

The study treatment names, abbreviations, and ordering to be used in the TFLs are presented in [Table 1](#).

Table 1: Presentation of Study Treatments in TFLs

Study Treatment	Abbreviation	Order in TFLs
200 mg LOXO-305 (Fasted)	A	1
200 mg LOXO-305 (Fed)	B	2
200 mg LOXO-305 + 40 mg Omeprazole (Fasted)	C	3
40 mg Omeprazole alone (Fasted)	OMP alone	4

The study treatment sequence names, abbreviations, and ordering to be used in the TFLs are presented in [Table 2](#).

Table 2: Presentation of Study Treatment Sequences in TFLs

Study Treatment Sequence	Abbreviation	Order in TFLs
200 mg LOXO-305 (Fasted) on Day 1/ 200 mg LOXO-305 (Fed) on Day 8/ 40 mg Omeprazole (Fasted) on Days 15 to 17/ 200 mg LOXO-305 + 40 mg Omeprazole (Fasted) on Day 18	A/B/C	1
200 mg LOXO-305 (Fed) on Day 1/ 200 mg LOXO-305 (Fasted) on Day 8/ 40 mg Omeprazole (Fasted) on Days 15 to 17/ 200 mg LOXO-305 + 40 mg Omeprazole (Fasted) on Day 18	B/A/C	2

All treatments described above are the planned treatments. The TFLs will reflect the actual treatments received.

7. DEFINITIONS OF POPULATIONS

Any protocol deviations will be considered prior to database lock for their importance and taken into consideration when assigning subjects to populations.

7.1. All Subjects Population

The all subjects population will include all subjects who signed the ICF and had any study assessment recorded in the database per the protocol.

7.2. Safety Population

The safety population will include all subjects who received at least 1 dose of study treatment (LOXO-305). Subjects will be classified into groups based on actual treatment received.

7.3. Pharmacokinetic Population

The PK population will include all subjects who received at least 1 dose of LOXO-305, have at least 1 quantifiable PK concentration, and for whom at least 1 PK parameter can be computed. A subject may be excluded from the PK summary statistics and statistical analysis if the subject has an AE of vomiting that occurs at or before 2 times the median t_{max} .

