2.2. Endpoints

The following PK parameters will be calculated whenever possible, based on the plasma concentrations of LOXO-305 (as appropriate):

- area under the concentration-time curve from Hour 0 to 24 hours postdose, as calculated by the linear trapezoidal method (AUC₀₋₂₄)
- area under the concentration-time curve from Hour 0 to the last measurable concentration (AUC_{0-t})
- area under the concentration-time curve extrapolated to infinity (AUC_{0-inf})
- extrapolation for area under the concentration-time curve (%AUC_{extrap})
- maximum observed plasma concentration (C_{max})
- time to maximum observed concentration (t_{max})

- apparent terminal elimination rate constant (λ_Z)
- apparent systemic clearance (CL/F)
- apparent terminal elimination half-life $(t_{1/2})$.

No value for AUC_{0-inf} , CL/F, or $t_{\frac{1}{2}}$ will be reported for cases that do not exhibit a terminal log linear phase in the concentration-time profile.

No PK parameters will be calculated for subjects with 2 or fewer consecutive timepoints with quantifiable concentrations.

Individual and mean plasma concentration-time curves (both linear and log linear) will be included in the final report.

Safety and tolerability will be assessed by monitoring AEs, performing physical examinations and clinical laboratory tests, measuring vital signs, and 12-lead ECGs.

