4.5. Subject Number and Identification

Subject numbers will consist of 6 digits in which the first set of 3 digits will identify the site and the second set of 3 digits will identify the subject (eg, 001-101). If subjects are withdrawn by the Investigator (or designee) or voluntarily withdraw prematurely from the study, replacement subjects may be enrolled only if deemed necessary by the Sponsor. If necessary, as determined by the Sponsor, subjects who fail to complete the treatment or have insufficient PK data may be replaced. Replacement subjects will be assigned a subject number by adding 100 to the last 3 digits of the subject number for the subject they are replacing (eg, Subject Number 001-201 replaces Subject Number 001-101).

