8.5.1.1. Criteria for Handling Concentrations Below the Limit of Quantification in Pharmacokinetic Analysis

Concentration values that are below the level of quantification (BLQ) will be set to zero, with defined exceptions as follows;

- Any embedded BLQ value (between 2 quantifiable concentrations) and BLQ values following the last quantifiable concentration in a profile will be set to missing for the purposes of PK analysis.
- If there are late positive concentration values following 2 BLQ concentration values in the apparent terminal phase, these values will be evaluated. If these values are considered to be anomalous, they will be set to missing.
- If an entire concentration-time profile is BLQ, the profile will be excluded from the PK analysis.
- If a predose concentration is missing, it may be set to zero in PK analysis by default within Phoenix WinNonlin.

8.5.1.2. Criteria for the Calculation of an Apparent Terminal Elimination Rate Constant and Half-Life

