8.5.1.3. Calculation of AUC

The minimum requirement for the calculation of AUC will be the inclusion of at least 3 consecutive plasma concentrations above the lower limit of quantification, with at least one of these concentrations following C_{max} .

For any partial AUC determination (eg. AUC_{0-24}), nominal time will generally be used for the end of the interval. Actual times for partial AUC intervals may be used at the discretion of the Pharmacokineticist.

AUC_{0-inf} values where the percentage extrapolation is less than 20% will be reported. AUC_{0-inf} values where the percentage extrapolation is between 20 to 30% will be flagged and included in the summary statistics and statistical analysis, whilst AUC_{0-inf} values where the percentage extrapolation is >30% will be reported but excluded from summary statistics and statistical analysis.

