8.5.1.4. Anomalous Values

If a value is considered to be anomalous due to being inconsistent with the expected PK profile, it may be appropriate to exclude this point from the PK analysis. However, the exclusion of data must have strong justification and will be documented in the raw data and the CSR.

Embedded BLQ values may be considered anomalous depending on the route of administration and the characteristics of the drug.

Subjects with positive predose values >5% of C_{max} may be excluded from the summary statistics and statistical analysis at the discretion of the Pharmacokineticist.

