8.5.4. Pharmacokinetic Statistical Methodology

All PK concentrations and parameters will be listed.

Summary tables, mean (+ SD) figures, overlaying individual figures, and individual figures by treatment and time postdose will be provided for plasma PK concentrations. All PK concentration figures will be produced on both linear and semi-logarithmic scales, with the exception of figures across all days, which will be produced on the linear scale only. The +SD bars will only be displayed on the linear scale.

Summary tables by treatment will be provided for all PK parameters, with the exception of diagnostic regression-related PK parameters. Summary statistics (n, Mean, SD, CV%, minimum, median, maximum, geometric mean [Geom Mean] and geometric CV% [Geom CV%]) will be calculated for plasma LOXO-305 PK parameters. Excluded subjects will be listed in the PK parameter tables, but will be excluded from the summary statistics and noted as such in the tables.

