8.5.4.1. Statistical Analyses

A statistical analysis will be conducted to investigate the food effect on the single dose administration of LOXO-305 and the drug-drug interaction of Omeprazole on the PK of LOXO-305 for AUC_{0-24} , AUC_{0-t} , AUC_{0-inf} , and C_{max} . The comparisons of interest are:

- 200 mg LOXO-305 (Fed) (test treatment) vs '200 mg LOXO-305 (Fasted) (reference treatment) i.e. Treatment B Vs Treatment A
- 200 mg LOXO-305 + 40 mg Omeprazole (Fasted) (test treatment) vs 200 mg LOXO-305 (Fasted) (reference treatment) i.e. Treatment C Vs Treatment A

The natural log (ln)-transformed³ PK parameters will be analyzed using a mixed model.⁴ The model will include planned treatment sequence, and actual treatment as fixed effects, and subject within planned treatment sequence as a random effect.

For each PK parameter separately, the least squares mean (LSM) for each treatment, difference in LSMs between the fed and fasted treatments, and corresponding 90% confidence interval (CI) will be calculated; these values will then be exponentiated to give the geometric least square means (GLSM), geometric mean ratios (GMR), and corresponding 90% CIs.

[figure not shown]
This procedure is equivalent to Schuirmann's⁵ two one-sided tests at the 0.05 level of significance.

Additionally, the pooled estimate (across all treatments) of the within-subject CV will be calculated, and residual plots will be produced to assess the adequacy of the model(s) fitted.

Example of the SAS code that will be used are as follows:

Mixed Model Analysis

CCI

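### Does the vomiting rule, which names the subject and not the treatment period, put valid PK profiles at risk?

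*SAP*

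**What the plan says.** The rule stands in the definition of the PK population in SAP 7.3, and in the same words in Protocol 8.2.1: "A subject may be excluded from the PK summary statistics and statistical analysis if the subject has an AE of vomiting" within twice the median tmax. It uses may, and it gives no period, treatment or profile as the unit.

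Under Protocol 5.3 each subject receives Treatments A, B and C once. SAP 8.5.4.1 compares B with A (food) and C with A (omeprazole) in a mixed model with "subject within planned treatment sequence as a random effect".

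Other passages bear on the unit:

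- Protocol 2.2: "No PK parameters will be calculated for subjects with 2 or fewer consecutive timepoints with quantifiable concentrations".
- SAP 8.5.1.1: "If an entire concentration-time profile is BLQ, the profile will be excluded from the PK analysis".
- SAP 8.5.1.3: AUC0-inf values with more than 30% extrapolation "will be reported but excluded from summary statistics and statistical analysis".
- SAP 8.5.1.4: subjects whose predose value exceeds 5% of Cmax may be left out of the summaries and the analysis at the pharmacokineticist's discretion.
- SAP 8.5.4, on parameter tables presented by treatment: "Excluded subjects will be listed in the PK parameter tables, but will be excluded from the summary statistics", and this is to be noted in the tables.

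**The concern.** In a crossover, vomiting soon after one dose compromises that dose's profile and says nothing about the profiles from the other periods. A rule that removes the subject could therefore throw away good data:

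- Vomiting after C would take valid A and B profiles out of the food comparison.
- Vomiting after B would take valid A and C profiles out of the omeprazole comparison.

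The loss would be needless, because a model with a random subject effect can use subjects with incomplete periods. The SAP also shows that it can write a narrower unit when it wants one, as in the rule for profiles entirely below the limit of quantification. At stake is the precision of one of the two primary comparisons, in a study whose sample size has no power basis.

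**Working it through.** **Which unit do the documents mean?** Three features point to the profile.

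1. The window is a multiple of tmax, so it is counted from one particular dose.
2. The predose rule in SAP 8.5.1.4 is the closest parallel. It too says that subjects may be excluded from the summaries and the analysis, yet the ratio of a predose value to Cmax exists only within one profile.
3. The minimum-data rule in Protocol 2.2 also says subjects, although consecutive quantifiable timepoints belong to one profile.

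So the documents use subject loosely for criteria that apply to a single dose. None of this states the unit for vomiting, but dropping one profile is within the text.

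**What would the harshest reading cost?** There is no figure in the plan to reproduce. Assumptions: N of 8, 12, 16 or 24 (the planned number is redacted); within-subject CV of 20% or 30% (none is given); one affected subject; no replacement.

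Take vomiting after C and its effect on B/A. Under the SAP model (sequence and treatment fixed, subject random) the variance of the log difference is 2σ²/n, where n is the number of subjects with both A and B.

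- Only the C profile dropped: n = N, so the standard error does not change.
- Whole subject dropped: n = N − 1, so the standard error is multiplied by √(N/(N−1)).

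The upper 90% limit divided by the geometric mean ratio is exp[t(0.95, df) × σ × √(2/n)], with σ = √ln(1 + CV²) and df = observations − subjects − 2. At CV 30%, σ = √ln(1.09) = 0.2936.

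Worked case, N = 8:

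- Profile dropped: 23 observations, 8 subjects, df = 13, t = 1.771. exp(1.771 × 0.2936 × √(2/8)) = 1.297.
- Subject dropped: 21 observations, 7 subjects, df = 12, t = 1.782. exp(1.782 × 0.2936 × √(2/7)) = 1.323.

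| Assumed N | Rise in SE, subject dropped | Limit factor, CV 30%: profile v subject dropped | Limit factor, CV 20%: profile v subject dropped |
|---|---|---|---|
| 8 | √(8/7) = 1.069, 6.9% | 1.297 v 1.323 | 1.192 v 1.208 |
| 12 | √(12/11) = 1.044, 4.4% | 1.229 v 1.241 | 1.149 v 1.157 |
| 16 | √(16/15) = 1.033, 3.3% | 1.193 v 1.200 | 1.126 v 1.131 |
| 24 | √(24/23) = 1.022, 2.2% | 1.153 v 1.157 | 1.101 v 1.103 |

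Vomiting after B has the same effect on C/A under this model. Variations:

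- With the period term that Protocol 8.3.2 includes, the rises for B/A after vomiting under C are 8.0%, 4.9%, 3.5% and 2.2%, against 0% if only the profile is dropped.
- Vomiting after A, the reference for both comparisons, damages both whatever the unit. Keeping B and C saves only 1.7–2.1% of the standard error at N = 8 and 0.6–0.7% at N = 24 (intra-subject correlation 0.5 to 0.9).
- With two subjects vomiting after B, dropping both entirely makes the log-scale 90% interval for C/A wider than dropping their B profiles alone, by 12.8% at N = 10 and 4.6% at N = 24 (between-subject CV of 40% assumed).

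**The case for a change.** The strongest case for an edit is that the rule sits in a population definition, and SAP 8.1 runs its analyses on the subjects assigned to each population, so the whole-subject reading is natural. An unstated unit also leaves a choice in the primary analysis open, in an open-label study. The edit would take one sentence. Replacement might not rescue the numbers, because Protocol 4.5 says only that "subjects who fail to complete the treatment or have insufficient PK data may be replaced", as the sponsor decides.

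It stands that the unit is not written down, and a clarifying sentence would do no harm. The rest carries less weight. May requires no exclusion, so no valid profile has to be lost. The trigger is a recorded adverse event in a fixed window, and excluded subjects must be shown and marked in the tables, so a reader could see what was done. SAP 8.5.1.4 adds that "the exclusion of data must have strong justification and will be documented in the raw data and the CSR". That sentence concerns anomalous values and not vomiting, so it supports the general practice without settling this rule.

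A tidy edit is also less simple than it looks. Rewording the vomiting rule alone would leave the predose rule in SAP 8.5.1.4 with the same loose unit and make it look deliberately subject-level. Which treatment's median tmax defines the window is a separate open detail. Settling it in the same sentence could change who qualifies for exclusion.

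**Conclusion.** No change is needed. This is a gap in drafting that analysts will fill sensibly, by setting aside the affected profile and letting the mixed model use the other two.

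The cost arises only if three things coincide: vomiting inside the window, a decision to exclude, and a choice to discard the subject's other periods as well. For one such subject, the untouched comparison then loses 6.9% in standard error at N = 8, falling to 2.2% at N = 24, under the SAP model with no replacement. The estimate stays free of systematic bias provided that the treatment ratio does not differ between subjects who vomit and those who do not. No decision in the documents turns on a change of that size, and SAP 8.1 already advises caution because the sample size is not based on power.

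The sizes rest on assumed N and CV. The documents give no vomiting rate for healthy subjects. Vomiting is not among the events listed for more than 10% of the 28 patients in Protocol 1.3.1, which is only indirect evidence.

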8. STATISTICAL METHODOLOGY

8.1. General

Listings will be provided for all data captured in the database. Listings will include all subjects assigned to the all subjects population and include data up to the point of study completion or discontinuation. Subjects are generally considered to have completed the study if they completed all protocol-specified procedures and assessments for the end-of-treatment visit. Any subject who discontinued the study will be identified accordingly in the listings. Summaries and statistical analyses will include the subjects assigned to the relevant population based on data type.

Data analysis will be performed using the SAS® statistical software package Version 9.4 (or higher if upversioned during the study).

Analysis Data Model (ADaM) datasets will be prepared using Clinical Data Interchange Standards Consortium (CDISC) ADaM Version 2.1 (or higher if upversioned during the study) and CDISC ADaM Implementation Guide Version 1.2 (or higher if upversioned during the study). Pinnacle 21 Community Validator Version 2.2.0 (or higher if upversioned during the study) will be utilized to ensure compliance with CDISC standards.

Caution should be used when interpreting results from the statistical analyses conducted in this study because the sample size is not based on power calculations.

Where reference is made to 'all calculations', this includes, but is not limited to, summary statistics, statistical analyses, baseline derivation, and changes from baseline.

